17. APPENDIX F – REDO PROCEDURAL CRF

1

2 **1. SYNOPSIS**

3 This prospective, single-center observational study aims to compare the clinical performance,
4 workflow efficiency, and electrophysiological metrics of two commercially available, high-
5 density multielectrode mapping catheters (Ostaray and Optrell) in patients undergoing catheter
6 ablation for complex atrial arrhythmias.

7 The primary focus is to determine if the real-time vector propagation capabilities of the Optrell
8 catheter combined with V8 software can accurately confirm conduction block across linear
9 ablation lesions without the need for full-chamber activation remapping, which is the current
10 standard of care. A secondary focus will pair-compare the bipolar voltage amplitude distributions
11 recorded by both catheters, given their differing electrode sizes and spacing

12

13 **2. BACKGROUND AND RATIONALE**

14 **2.1 The Clinical Challenge of Conduction Block Assessment**

15 Catheter ablation is a cornerstone therapy for atrial fibrillation (AF) and atrial flutter. In patients
16 with persistent AF or specific anatomical flutters, the creation of linear ablation lesions (e.g., roof
17 line, posterior wall isolation, cavotricuspid isthmus [CTI] line, or mitral isthmus line) beyond
18 standard Pulmonary Vein Isolation (PVI) is often clinically indicated.

19 A critical determinant of procedural success and long-term freedom from arrhythmia is the
20 achievement of bidirectional conduction block across these lines. Currently, confirming this block
21 requires time-consuming, full-chamber activation remapping using a standard high-density
22 catheter (such as the Ostaray).

23 **2.2 The Investigational Approach**

24 The Optrell catheter, when integrated with V8 mapping software, offers real-time visualization of
25 electrical propagation vectors. We hypothesize that this directional vector mapping allows
26 operators to immediately and accurately identify the presence or absence of conduction block
27 across a linear lesion. Validating this hypothesis could eliminate the need for complete chamber
28 remapping, significantly streamlining procedural workflow and reducing procedure times.

2.3 Voltage Amplitude Comparison Bipolar voltage amplitude is the standard metric for defining healthy myocardium versus atrial scar tissue. However, measured voltage is heavily dependent on catheter design, specifically electrode size and inter-electrode spacing. Because the Octaray and Optrell catheters differ in these physical properties, it is essential to establish how their voltage readings correlate and whether catheter-specific voltage cutoffs are necessary for accurate scar delineation.

2.4 Regulatory Status All equipment utilized in this study, including the Octaray and Optrell catheters and their associated mapping systems, are fully approved for clinical use by the FDA, CE, and AMAR (Israeli Ministry of Health) and are routinely utilized in standard practice at our institution.

3. STUDY OBJECTIVES

3.1 Primary Objective

To evaluate the diagnostic concordance and workflow efficiency of real-time vector-based assessment using the Optrell catheter (with V8 software) compared to standard full-chamber activation mapping for confirming bidirectional conduction block across atrial ablation lines.

3.2 Secondary Objectives

- To perform a paired comparison of bipolar voltage amplitude distributions in the left atrium recorded by the Optrell versus the Octaray catheter during CS pacing before and after ablation.
- To perform a paired comparison of multipolar voltage amplitude distributions in the left atrium recorded by the Optrell versus bipolar voltage with the Octaray catheter during CS pacing before and after ablation.
- To evaluate the safety profile of the dual-catheter mapping approach.
- To assess long-term clinical outcomes, specifically the 12-month freedom from recurrent atrial tachyarrhythmias (AF, atrial flutter, or atrial tachycardia).

4. STUDY ENDPOINTS

4.1 Primary Endpoints

- **Concordance:** Percentage of agreement (presence vs. absence of bidirectional block) between the Optrell real-time vector assessment and standard activation remapping on a per-line basis.
- **Workflow Efficiency:** Difference in time (in minutes) required to confirm conduction block status using the Optrell vector method versus full activation mapping.

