6.2 Intra-Procedural Workflow

The procedure will be performed under general anesthesia. Following standard venous access, transseptal puncture will be performed to access the left atrium. Systemic anticoagulation with intravenous Heparin will be administered and maintained to achieve an activated clotting time (ACT) >300 seconds.

• Phase 1: Voltage Mapping (coronary sinus pacing)

Following transseptal access and prior to ablation, a left atrial 3D map using TPI with left atrial voltage mapping will be performed using the Octaray catheter. The Octaray catheter will then be exchanged for the Optrell catheter, and a second high-density voltage map will be acquired on the

same 3D map (remap). A high density Multipolar map using parallel mapping will be performed in the same time with the Optrell catheter. All the maps need to have a fill threshold $\leq 3\text{mm}$ to allow sufficient density.

For patient in atrial fibrillation, an electrical cardioversion will be performed and mapping will be performed during coronary sinus pacing. For patient in sinus rhythm, mapping will be performed during coronary sinus pacing. For patient in atrial flutter, mapping will be performed in arrhythmia.

• **Phase 2: Ablation:**

The operator will perform PVI and any clinically indicated linear lesion sets according to standard of care using either radiofrequency or pulsed field ablation energy.

• **Phase 3: Conduction Block Assessment**

After completing the ablation phase, conduction block across lines will be assessed using both methods:

- *Optrell Vector Assessment*: Real-time evaluation of conduction vectors using the Optrell catheter and V8 software. The time to determination, from the beginning of the mapping (pacing start) to block confirmation, and the binary result (block vs. no block) will be recorded.
- *Standard Activation Mapping*: Creation of a full activation map using the Octaray catheter (often requiring pacing maneuvers) to establish the gold-standard confirmation of block. Time to determination, from the beginning of the mapping to block confirmation, and the binary result will be recorded.

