8.2 Efficacy Analyses

• **Concordance of Block:** Agreement between the vector-based assessment and standard activation mapping will be evaluated using absolute percentage agreement and Cohen's Kappa statistic for inter-method reliability.

• **Time to Confirmation:** The time required to confirm conduction block will be compared between the two methods using a paired t-test or Wilcoxon signed-rank test, depending on the normality of the data distribution.

• **Voltage Comparison:** Paired continuous voltage data from the Octaray and Optrell catheters will be analyzed using Pearson or Spearman correlation coefficients. Furthermore, Bland-Altman analysis will be conducted to assess for systematic bias and establish limits of agreement between the two catheter designs.

• **Clinical Outcomes:** Freedom from arrhythmia at 12 months will be analyzed using Kaplan-Meier survival estimates.

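### The primary concordance endpoint does not separate missed gaps from false gaps, although the question is accuracy against a named gold standard

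*Protocol*

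**What the plan says.** The Synopsis (Protocol, Section 1) gives the primary focus as whether the Optrell "catheter combined with V8 software can accurately confirm conduction block across linear" lesions; the sentence goes on "ablation lesions without the need for full-chamber activation remapping, which is the current" standard of care. Section 2.2 carries the idea further: operators would identify block or its absence "across a linear lesion. Validating this hypothesis could eliminate the need for complete chamber" remapping.

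Section 6.2, Phase 3, fixes the timing: "After completing the ablation phase, conduction block across lines will be assessed using both methods". The Octaray map is made "to establish the gold-standard confirmation of block", and Section 7.4 gives it the same role at redo procedures.

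The first primary endpoint (Section 4.1) is "Percentage of agreement (presence vs. absence of bidirectional block) between the Optrell real-time vector assessment and standard activation remapping on a per-line basis". Section 8.2 analyses it by "absolute percentage agreement and Cohen's Kappa statistic for inter-method reliability". The protocol names no sensitivity, specificity, predictive value or limit on missed gaps. It also states no expected block rate, gap rate or number of lines. Section 8.1 gives 30 patients, each likely to contribute several lines.

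**The concern.** A study that names a reference standard and asks whether a quicker test is accurate enough to stand in for it is asking a diagnostic-accuracy question. The two possible errors differ in kind. If the vectors call block where the Octaray map shows conduction, a gap is missed. If they call a gap where the map shows block, the cost is an unneeded check. Percentage agreement counts the two errors alike. Kappa corrects for chance but is also symmetric in the two methods.

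Lines are read after ablation aimed at block, so a high share of blocked lines is plausible, though the protocol gives no figure. In that setting agreement largely reflects how often block was achieved. The study could then report high concordance without stating the error rate that matters most for leaving out the remap.

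**Working it through.** **Inputs.** From the protocol: binary reading per method per line (Section 6.2, Appendix D), Octaray map as reference, 30 patients. Not in the protocol and therefore assumed: share of lines blocked (80 to 95%), 60 lines with 6 gaps for the worked table, and the accuracy values below. Section 8.1 gives no formula or precision target, so there is no planned figure to reproduce. Lines are treated as independent, which is optimistic because they cluster within patients.

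**Formulas.** With *p* the share of lines blocked, *sp* the share of blocked lines called block and *se* the share of gap lines called gap:

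- agreement: po = p × sp + (1 − p) × se
- share of lines that the vectors call block: v = p × sp + (1 − p)(1 − se)
- chance agreement: pe = p × v + (1 − p)(1 − v)
- kappa = (po − pe) / (1 − pe)

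**Step 1: a reader who always calls block** (sp = 1, se = 0). Here po = p, so agreement is 80%, 90% or 95% at p = 0.80, 0.90 or 0.95. Also pe = p, so kappa = 0 each time.

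**Step 2: half the gaps missed, 98% correct on blocked lines.** At p = 0.90: po = 0.882 + 0.050 = 0.932; v = 0.932; pe = 0.9 × 0.932 + 0.1 × 0.068 = 0.8456; kappa = 0.0864 / 0.1544 = 0.56. At p = 0.80 and 0.95, agreement is 88% and 96%, and kappa 0.57 and 0.51.

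**Step 3: accuracy held fixed** (98% on blocked lines, 90% on gaps). At p = 0.80: po = 0.964, pe = 0.6824, kappa = 0.2816 / 0.3176 = 0.89. At p = 0.95: po = 0.976, pe = 0.8924, kappa = 0.0836 / 0.1076 = 0.78. Kappa moves with prevalence alone.

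**Step 4: direction of error.** 60 lines, 54 blocked and 6 with gaps:

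| Vector result | Agreement | pe | Kappa | Gap sensitivity | Specificity | False share of block calls |
|---|---|---|---|---|---|---|
| 3 gaps missed, 0 false gaps | 57/60 = 95% | (54×57 + 6×3)/3600 = 0.86 | 0.09/0.14 = 0.64 | 3/6 | 54/54 | 3/57 = 5.3% |
| 0 missed, 3 false gaps | 57/60 = 95% | (54×51 + 6×9)/3600 = 0.78 | 0.17/0.22 = 0.77 | 6/6 | 51/54 | 0/51 |
| 0 missed, 6 false gaps | 54/60 = 90% | (54×48 + 6×12)/3600 = 0.74 | 0.16/0.26 = 0.62 | 6/6 | 48/54 | 0/48 |

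The first two rows have the same agreement, with gap sensitivity of 50% in one and 100% in the other. Comparing the first and third rows, both planned statistics rank the method that misses half the gaps above the one that misses none, because the latter makes more errors in total.

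**Step 5: precision on gaps.** If all n gap lines are detected, the exact two-sided 95% lower limit is 0.025^(1/n): 54% for n = 6 and 63% for n = 8. A lower limit of 80% needs n = 17 (0.025^(1/17) = 0.805), which means 17/0.10 = 170 lines at 10% gaps, 85 at 20% and 57 at 30%.

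**The case against.** **The endpoint matches the stated objective.** Section 3.1 asks for diagnostic concordance, and Section 4.1 measures concordance. The accuracy and replacement language sits in the Synopsis and background, the replacement sentence is conditional, and no success threshold or decision rule is set. A reader might infer that the protocol commits the study to dropping remapping on high agreement; it does not. What survives is that the Synopsis makes accuracy the primary focus and a gold standard is named, so the direction of error is defined but not reported.

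**Kappa is planned too.** A reader might infer that kappa, like agreement, is swamped by blocked lines. The figures do not support that. Kappa is 0 for the always-block reader, and in the examples above it lies at 0.51 to 0.57 when half the gaps are missed and at 0.78 to 0.89 when 90% are found. Its weaknesses are narrower: it mixes the two errors and varies with prevalence.

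**The data are there.** A reader might also infer that the study cannot show missed gaps. It can: Appendix D records both results for every line, with a concordance tick and room for an explanation, and Section 7.4 adds readings of prior lines before new ablation.

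**An SAP could add accuracy measures.** None is available here. Interval methods may fairly be left to it, but the headline measure is chosen in the protocol, and an SAP addition would only supplement it.

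**Conclusion.** The point holds as a mismatch between the question and the primary measure. Percentage agreement can reach 80 to 95% with every gap missed, if 80 to 95% of lines are blocked. Kappa exposes that extreme case, but neither statistic tells a missed gap from a false one, and in the 60-line example both favour the method that misses half the gaps.

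The percentages rest on assumed block rates and line counts, since the protocol states neither. The pooling of the two errors does not depend on those assumptions: it follows from the definition of the statistics. How few gap lines there will be is also unknown, and redo readings may add some. At the counts shown, even perfect detection leaves a lower limit of only 54 to 63%, so a firm replacement claim from 30 patients is unlikely unless gaps are common.

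**What to change.** In Sections 4.1 and 8.2:

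- Make the primary concordance result the per-line 2x2 table of Optrell against Octaray readings.
- Report gap sensitivity (Octaray no-block lines that Optrell also calls no block), specificity (Octaray block lines that Optrell calls block) and the share of Optrell block calls that are false, each with an exact or patient-clustered interval.
- Show the prior-line readings from redo procedures (Section 7.4) separately.
- Keep percentage agreement and kappa as descriptive results.
- State that any conclusion about omitting remapping rests on the lower limit of gap sensitivity, and is preliminary if gap lines are few.

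The table uses the two binary results already on the CRF, so it needs no new data. The cost is a less favourable headline with a wide interval. Restricting the analysis to readings taken before any touch-up is optional: the index CRF has one result per method per line, so it would need a small added field or a sequencing rule.

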Optrell bipolar	 Yes  No	 Yes  No	_____ points
Optrell multipolar	 Yes  No	 Yes  No	_____ points

SECTION 3: PHASE 2 - ABLATION DETAILS

Variable	Data Entry
Ablation Energy Used	 RFA  PFA
PVI Performed?	 Yes  No
PVI Successfully Achieved?	 Yes  No
First Pass Isolation ?	 Yes  No
Linear Lesions Created (Check all that apply)	 Roof Line  Posterior Wall Isolation (PWI)  Cavotricuspid Isthmus (CTI)  Mitral Isthmus Line  Other: _____

SECTION 4: PHASE 3 - CONDUCTION BLOCK ASSESSMENT

(Complete this sub-section for EVERY linear lesion created. See Section 4b, 4c and 4d. Duplicate if necessary.)

Line Checked	 Roof Line  Posterior Wall Isolation (PWI)  Cavotricuspid Isthmus (CTI)  Mitral Isthmus Line  Other:	
Ablation Energy Used	 RFA  PFA	

Assessment Method	Time to Verify Block	Block Confirmed?
Optrell Vector Assessment (time to assess block by moving the catheter across the line to review vectors)	___ min : ___ sec	 Yes  No
Octaray Activation Mapping (time to create an activation map sufficient to determine presence or absence of block)	___ min : ___ sec	 Yes  No

Concordance for this line: ☐Yes (Methods agree) ☐No (Methods disagree)

Explain:_____

SECTION 5: ACUTE PROCEDURAL COMPLICATIONS (completed at hospital discharge)

Variable	Data Entry
None	
Pericardial Effusion / Tamponnade	
Stroke / TIA	

CONFIDENTIAL

Variable	Data Entry
Vascular Complication requiring intervention	
Phrenic Nerve Injury	
Prolongation of Hospitalization (>24 hours beyond the expected post-procedural course)	
Esophageal injury	

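### The primary time endpoint sets a chamber-level Octaray map against a line-level vector check on per-line forms, with no unit of analysis and no rule for a map that covers several lines

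*Protocol*

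**What the plan says.** Section 3.1 of the protocol sets the vector assessment against a chamber-level standard: "compared to standard full-chamber activation mapping for confirming bidirectional conduction block across atrial ablation lines". Section 4.1 then lists two primary endpoints. Concordance is agreement "between the Optrell real-time vector assessment and standard activation remapping on a per-line basis". The time endpoint is "Difference in time (in minutes) required to confirm conduction block status using the Optrell vector method versus full activation mapping", with no unit attached.

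Section 6.2 (Phase 3) describes the Octaray step as "Creation of a full activation map using the Octaray catheter (often requiring pacing maneuvers) to establish the gold-standard confirmation of block", timed from the start of mapping until block is confirmed. The Optrell clock runs "from the beginning of the mapping (pacing start) to block confirmation". Section 7.4 repeats both definitions for redo procedures.

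Appendix D, Section 4, carries the instruction "Complete this sub-section for EVERY linear lesion created". Each copy of the form has two time fields for one named line. The Optrell field is the time to move the catheter over that line and read the vectors. The Octaray field is the "time to create an activation map sufficient to determine presence or absence of block". Appendix F does the same for redo procedures. Neither appendix has a field for the start and stop of a map, or for the lines that a map covered.

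Section 8.1 expects several lines per patient. Section 8.2 names a paired t-test or its Wilcoxon counterpart, without saying whether the pair is a line or a patient. Section 2.2 gives the purpose: to avoid remapping the chamber and so shorten the procedure.

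**The concern.** The two times belong to different units. A full activation map is made of a chamber and may settle several lines in it. A vector check is made of one line and is repeated for the next. Placing both on a form for each line allows the same map time to be entered more than once, while each vector time is entered only once.

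The comparator is also described in two ways. A full map takes at least as long as one that is merely sufficient to judge a line, so the choice of definition affects the size of the saving.

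At stake is the meaning of a primary endpoint. A shorter procedure is a property of the patient's procedure as a whole, and an average over line forms need not estimate it.

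**Working it through.** The protocol gives no expected time for either method, no line count per chamber and no effect size for this endpoint, so there is no stated figure to reproduce. The check is algebra with assumed times.

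**Inputs**
- T: time of one Octaray map of a chamber (assumed; 5, 10 and 15 min tried).
- v: vector time per line (assumed; 2, 3 and 4 min tried).
- k: lines in that chamber settled by the one map. Section 8.1 expects several lines per patient but gives no number. Appendix D names three left atrial options (roof, posterior wall, mitral isthmus), so k = 2 or 3 is possible there. A cavotricuspid isthmus line lies in the right atrium and would not share a left atrial map.

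**Formulas, if T is entered on each of the k forms**
- Recorded saving per line: T − v.
- Real saving per chamber: T − kv. Per line: T/k − v.
- Overstatement per line: (T − v) − (T/k − v) = T(1 − 1/k), which is 0 at k = 1, 50% of T at k = 2 and 67% of T at k = 3.
- Wrong sign only if T − v > 0 and T/k − v < 0, that is, T/k < v < T.

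**Main illustration, T = 10 and v = 3 (minutes)**

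| k | Recorded per line | Real per line | Real per chamber | Overstatement per line |
|---|---|---|---|---|
| 1 | 7 | 7 | 7 | 0 |
| 2 | 7 | 10/2 − 3 = 2 | 10 − 6 = 4 | 5 |
| 3 | 7 | 10/3 − 3 = 0.33 | 10 − 9 = 1 | 6.67 |

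The sign is right in every row. With T = 10, reversal would need v above 5 min at k = 2, or above 3.33 min at k = 3.

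**Range over other assumed times**

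| T | v | k | Recorded per line | Real per line | Real per chamber |
|---|---|---|---|---|---|
| 10 | 2 | 2 | 8 | 3 | 6 |
| 10 | 2 | 3 | 8 | 1.33 | 4 |
| 10 | 4 | 3 | 6 | −0.67 | −2 |
| 15 | 4 | 2 | 11 | 3.5 | 7 |
| 15 | 4 | 3 | 11 | 1 | 3 |
| 5 | 2 | 2 | 3 | 0.5 | 1 |
| 5 | 2 | 3 | 3 | −0.33 | −1 |

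**The line set given as an example in section 8.1** (roof, posterior wall, cavotricuspid isthmus). Assume a left atrial map of 10 min shared by two lines, a right atrial map of 5 min for one, and v = 3. The recorded savings are 7, 7 and 2, with mean 16/3 = 5.33 min per line. The real saving is 10 + 5 − 9 = 6 min per patient, or 2 min per line.

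**Separate maps.** If each line has its own map, the recorded saving equals the real one and the bias is zero.

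**The case against.** The strongest reply is that the protocol describes no double counting. Nowhere does it say that one map serves several lines, or that its whole time goes on each form. Section 6.2 notes that pacing manoeuvres are often needed, so separate acquisitions per line are possible. On a form for one named line, the Octaray field can be read as that line's own time. The per-line unit is stated for concordance only, so an analysis plan could still choose the patient as the unit for time.

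Much of this stands. A reader might infer that the saving *is* overstated, or that its sign *will be* wrong. The documents do not support either: both need a shared map, its full time entered on each form and an analysis by line, and a reversal also needs a vector time that is long relative to T/k.

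Two other tempting readings are weak. One is that a line without block never stops the clock. However, section 6.2 speaks of time to determination and records a result of block or no block, so mention of confirmation alone is loose wording. The other is that the clocks start at different events because only the Optrell clock mentions pacing. Both are said to start when mapping begins.

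The reply does not remove the data-capture problem. Three forms each showing 10 minutes could mean one shared map or three maps, and three forms each showing about 3 minutes could be one map divided. A later analysis plan cannot tell these apart, because the form does not ask. The difference between a full and a sufficient map is also on the page.

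**Conclusion.** The point holds in conditional form. The protocol sets a chamber-level time against a line-level time on line-level forms. It gives the time endpoint no unit, cannot show that a map was shared, and defines the Octaray time in two ways.

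Where a map is shared, its time is entered in full on each form and the analysis is by line, the overstatement is T(1 − 1/k) per line. That is half the map time at two lines and two thirds at three. It is zero with one line per chamber or one map per line. All minutes used here are assumptions; the percentages are not, given sharing. How often maps will be shared cannot be known from the document, though a full-chamber comparator and several expected lines per patient make it a realistic case. A reversed sign is possible only when T/k < v < T and should not be presented as the expected result.

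The matter should be settled before data collection, since the information needed to correct it later would not exist.

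**What to change.** - Define the primary time endpoint per patient: the total time by each method to determine the status, block or no block, of all lines. Include patients with at least one assessed line, since section 5.1 admits patients whose lines are only planned or anticipated.
- In Appendices D and F, record start and stop once per Octaray map, list the lines it covers, and count that time once.
- Use the same start and stop events for both methods, with the stop at status determined.
- Choose one definition of the Octaray comparator, full or sufficient, and use it in sections 4.1, 6.2 and 7.4 and in the CRF.
- Apply the paired test in section 8.2 to patient-level differences and keep per-line times descriptive.

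The cost is a revision of the CRF and of the endpoint wording, with no extra mapping. The reported saving may be less favourable than a per-line figure would be.
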